## 1. BACKGROUND

The IDx-DR device is intended to be used by health care providers to automatically screen for more than mild diabetic retinopathy (mtmDR). The IDx-DR outputs correlate with levels of disease identified in the America Academy of Ophthalmology's Preferred Practice Pattern (AAO PPP), which are associated with well-characterized management recommendations [1]. According to the AAO PPP, patients presenting with mtmDR have a level of disease associated with management recommendations outside of the normal 12-month screening period for patients with diabetes, and the physician overseeing the exam is advised to refer them to an eye care provider.

The IDx-DR Device, will produce a report for the physician overseeing the exam. IDx-DR will produce **one** of three outputs:

1. The IDx-DR result MORE THAN MILD DIABETIC RETINOPATHY DETECTED: REFER TO AN EYE CARE PROFESSIONAL indicates the presence of more than mild diabetic retinopathy, which includes moderate non-proliferative diabetic retinopathy, severe non-proliferative retinopathy (NPDR), proliferative retinopathy (PDR), and/or macular edema. Per the AAO PPP, patients with mtmDR have a level of disease associated with management recommendations outside of the normal 12-month screening period for patients with diabetes, and the physician overseeing the exam is advised to *refer* them to an eye care provider.
2. The IDx-DR result of NEGATIVE FOR MORE THAN MILD DIABETIC RETINOPATHY: RESCREEN IN 12 MONTHS will indicate that IDx-DR did not detect macular edema, moderate non-proliferative retinopathy, severe non-proliferative retinopathy, or proliferative retinopathy. Per the AAO PPP, it is recommended that patients be *rescreened annually*.
3. The IDx-DR report will indicate EXAM QUALITY INSUFFICIENT when the IDx-DR Exam Quality Index determines that the result should not be provided to the user due to insufficient fundus image quality submitted for analysis. The Exam Quality Index threshold was designed to determine when disease cannot be effectively ruled out from a set of exam images. The device will give the user guidance on what images caused the problem so the user can take action to efficiently re-image the patient either non-mydratically or in conjunction with the use of pharmacologic dilation. Guidance to the user will be expressed as "Insufficient Quality" (an indication of dark or obscured images) or "Protocol Failure" (an indication that the submitted images do not adhere to the protocol of one fovea centered and one macula centered image per eye). Patients who are unable to receive a result other than "EXAM QUALITY INSUFFICIENT" after reimaging will ultimately be recommended for *referral* to an eye care professional in product labeling.

In rare cases, the IDx-DR Device may also produce a result of "Technical Failure – Exam not Suitable for Analysis." This occurs when the exam submitted is of such poor quality that IDx-DR is unable to recognize submitted images as fundus photographs and therefore cannot analyze the image due to insufficient quality. Note that this result is different from "Exam Quality Insufficient," which is a result where the IDx-DR exam quality index is designed to override a diagnostic result that would otherwise be produced.

The IDx goal is to deliver a level of performance that aligns with the FDA's target that the IDx-DR Device rule out lower bounds of at least 75% sensitivity and at least 77.5% specificity for the mtmDR configuration, with study success defined as achieving at least 80% sensitivity and at least 80% specificity.

All diagnoses will be made according to the Fundus Photograph Reading Center (FPRC).

## 2. PROTOCOL OVERVIEW

### 2.1. Study Design

#### 2.1.1. Prospective Cohort

This is a multi-center pivotal study for registration purposes. Study subjects (n=845 after exclusions) [REDACTED] will be recruited at primary care sites. Between 10 and 15 independent primary care sites will participate in the study.

#### 2.1.2. Enriched Cohort

At the start of the study all participants with diabetes who meet inclusion and exclusion criteria will be enrolled. To avoid excessive enrollment in any one stratum (no/mild, mDR, or vtDR), the totals will be monitored monthly [REDACTED].

The impact of enrichment [REDACTED] is not known. The goal will be to recruit enough subjects to satisfy each stratum. [REDACTED].

Monitoring of strata will be performed by the statistician while maintaining masking to IDx-DR results; [REDACTED].

#### 2.1.3. Precision Study

[REDACTED].

### 2.2. Independent Reading Center

The FPRC independent Reading Center will determine the reference standard for the severity of retinopathy and diabetic macular edema according to the Early Treatment of Diabetic Retinopathy Grading System (ETDRS) based on W-4 fundus photographs. Center involved macular edema will be assessed from OCT images according to the RC protocol, to be used for secondary endpoint analysis. Incidental findings and an indication of media opacity presence will also be documented.

### 2.3. Statistical Monitoring

The statistician will compare the performance of the IDx-DR device to FPRC readings in terms of sensitivity and specificity as well as Receiver Operator Characteristics for the device's mtmDR classifier algorithm. Results will also be monitored for enrichment outcomes.

### 3. STATISTICAL ASSUMPTIONS AND SAMPLE SIZE CALCULATIONS

#### 3.1. [REDACTED]

[REDACTED]

[REDACTED]

[REDACTED]

[REDACTED]

[REDACTED]

Per the FPRC's Grading Charter, the following table summarizes the conversion of ETDRS scores to ground truth for the study:

IDx-DR Output	AAO PPP	ETDRS DR Grades	ETDRS Macular Edema Determination		
No/Mild DR	Normal or Minimal NPDR	10, 12, 14A, 14B, 14C, 14Z, 15, 20			
	Mild NPDR				
mtmDR	Moderate NPDR	35A, 35B, 35C, 35D, 35E, 35F, 43A, 43B, 47A, 47B, 47C, 47D	Definite Criteria 1: zone of retinal thickening > 1DA, part < 1 DD from center		
	vtDR			Severe NPDR	Definite Criteria 2: retinal thickening or adjacent HE < 600 $\mu$ from center
				Non-high-risk PDR	
				High Risk PDR	
Macular Edema					

Note that subjects with a grade of 90 will be excluded from primary analysis as being "ungradable" by FPRC for diabetic retinopathy severity level.

[REDACTED]

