### 3.6. Key Assumptions

The following assumptions govern sample size:

- [REDACTED]  
[REDACTED].
- The algorithms will be locked prior to subject enrollment.
- [REDACTED].
- The primary population for analysis will be patients from the Intention to Screen (ITS) population that have an IDx-DR result and a reference standard from the Reading Center.
- [REDACTED]  
[REDACTED]  
[REDACTED].
- To address incomplete data, prospective rules for case inclusion are summarized (see Section 4.7.7.2)

Both sensitivity and both specificity must achieve statistical significance to support study success. This strategy preserves the overall Type I error.

The statistical assumptions that were used to plan the study are as follows:

- Sample size calculations were performed at the subject-level.
- Use of conservative one-sided hypothesis testing with overall one-sided 2.5% Type I error [REDACTED]  
[REDACTED].
- The null hypotheses will be tested separately for mtmDR sensitivity and mtmDR specificity.
- All combined mild DR + no DR subjects will be included in the mtmDR specificity calculation. All mtmDR [REDACTED] subjects will be included in the more than mild DR sensitivity calculation.
- Subjects that received a IDx-DR result of "Insufficient Exam quality" will be excluded from primary analysis. [REDACTED]  
[REDACTED]  
[REDACTED]

[REDACTED]  
 [REDACTED]  
 [REDACTED]. As with all subjects, these subjects will also have been imaged using a 4-W protocol, with the wide field photos used by the FPRC to determine the reference standard.

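### As printed, the grade 90 exclusion removes subjects whom definite macular edema already makes mtmDR, so any with a device result leave the sensitivity denominator

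*SAP*

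**What the plan says.** The note under the conversion table in SAP 3.1 says that "subjects with a grade of 90 will be excluded from primary analysis". The reason it gives is that the Reading Center could not grade their DR severity. No exception is printed.

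The table has one column for ETDRS DR grades and another for the ETDRS macular edema determination. The second holds its own criteria, for example "Definite Criteria 1: zone of retinal thickening > 1DA, part < 1 DD from center". SAP 1 describes the positive device output as more than mild DR, "which includes moderate non-proliferative diabetic retinopathy, severe non-proliferative retinopathy (NPDR), proliferative retinopathy (PDR), and/or macular edema".

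SAP 2.2 says that the Reading Center "will determine the reference standard for the severity of retinopathy and diabetic macular edema", in both cases from the W-4 photographs. Center-involved edema seen on OCT is "to be used for secondary endpoint analysis".

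Four other places bear on who is counted:

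- SAP 3.6: all mtmDR (a redaction follows) "subjects will be included in the more than mild DR sensitivity calculation".
- SAP 3.2: all cases are to be accounted for in both co-primary measures.
- SAP 4.4.1: the ITS population needs eligibility and a Reading Center reference standard result. A DR severity grade is not named as a condition.
- SAP 4.1: primary-analysis subjects must be evaluable according to the Reading Center and have an IDx-DR screening result. The visible text does not define evaluable for a subject with ungradable severity and definite edema.

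**The concern.** The reason given for the exclusion covers one of the two routes to mtmDR, but the exclusion applies to the whole subject. When edema is definite, the missing severity grade leaves nothing in doubt about mtmDR status: the subject is positive at any grade. The rule therefore discards subjects whose reference status is known.

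The loss falls on one side only. A grade 90 subject without definite edema cannot be called negative, so excluding that subject is consistent with the table. Those with definite edema can only be positives, so the note acts on the sensitivity denominator and leaves specificity untouched. Sensitivity is co-primary, tested against 75% at one-sided 2.5% (SAP 3.7, 4.7.3). The set of positives that count should follow from the definition of mtmDR and not be left to interpretation at database lock.

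**Working it through.** **Step 1. The rule against the definition.** Take a subject with grade 90, definite edema on the W-4 photographs, and an IDx-DR result.

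| Source | Status of this subject |
|---|---|
| SAP 1, definition of mtmDR | positive |
| SAP 3.1, edema column | positive |
| SAP 3.6, sensitivity calculation | included, subject to the redaction |
| SAP 4.4.1, ITS | included, if the edema grading counts as a reference standard result |
| SAP 4.1, evaluability | not determined by the visible text |
| SAP 3.1, note | excluded from the primary analysis |

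The note cannot be reconciled with the definition for this subject.

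**Step 2. What the documents give for size.** There is no plan figure to reproduce. The total is 845 after exclusions (SAP 2.1.1). The visible text gives neither the split into mtmDR and no/mild DR nor a count of grade 90 subjects with edema. All figures below other than the 75% null and the 2.5% level are assumptions.

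**Step 3. Effect on the lower bound.** With x detected among n positives, the exact one-sided 97.5% lower bound L solves P(X ≥ x | n, L) = 0.025, so L is the 0.025 quantile of Beta(x, n − x + 1). The exact method is itself an assumption. Adding back k subjects, of whom d are detected, replaces x/n by (x + d)/(n + k). Start from 201/237.

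| k added | d detected | Sensitivity | Lower bound |
|---|---|---|---|
| 0 | – | 201/237 = 84.8% | 79.6% |
| 1 | 0 | 201/238 = 84.5% | 79.2% |
| 3 | 0 | 201/240 = 83.8% | 78.5% |
| 5 | 0 | 201/242 = 83.1% | 77.7% |
| 5 | 4 | 205/242 = 84.7% | 79.5% |
| 5 | 5 | 206/242 = 85.1% | 80.0% |

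The bound can move either way, depending on d.

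**Step 4. Other numbers of positives.** With 128/150 detected the bound is 78.6%. Adding 5 gives 75.7% if none is detected and 78.6% if 4 are. With 170/200 the bound is 79.3%, and the same additions give 77.1% and 79.2%.

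**Step 5. A result close to the pass mark.** With 237 positives, 192 detected is the fewest that passes. At 194/237 the bound is 76.3%. Adding 3 undetected subjects gives 194/240, bound 75.3%, still a pass. Adding 4 gives 194/241, bound 74.9%, a fail. This start was chosen to lie near the boundary.

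**Step 6. False success.** Suppose true sensitivity over all positives is exactly 75%, with 150 kept and 5 dropped. The kept subjects' sensitivity is (0.75 × 155 − 5s)/150, where s is sensitivity in the dropped five. The test on 150 passes at 124 or more.

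- s = 0: kept sensitivity 116.25/150 = 77.5%; chance of passing 0.075.
- s = 0.5: 113.75/150 = 75.8%; chance 0.028.
- s = 0.75: 75.0%; chance 0.016, the exact level of the test, within the nominal 0.025.

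**The case against.** **The governing rules are not all visible.** The table summarizes a Grading Charter that is not in the documents, a redacted block follows the note, and SAP 3.6 refers to case-inclusion rules in Section 4.7.7.2, which does not appear in the public text. Any of these may hold the exception. This stands. It is why the request is to correct the note or cross-reference the rule.

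**The group may be nearly empty.** A subject must be ungradable for severity on dilated W-4 photographs taken by a certified photographer (Protocol III), have definite edema on those same photographs, and have a device result. Edema seen only on OCT does not count. This stands too: zero is possible.

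**The bias may run in neither direction.** A reader might infer that these are hard-to-image eyes where the device performs worst, so that dropping them inflates sensitivity. The documents do not support that. Grade 90 describes the W-4 images, while the device reads separate NW400 images and withholds a result when their quality is too poor to rule out disease (SAP 1). Those insufficient-quality exams leave the primary analysis under a different rule (SAP 3.6). Poorer performance in the remainder is plausible but not shown.

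**One ungradable eye.** A reader might also infer that a subject with one grade 90 eye is dropped even when the fellow eye shows moderate or worse disease. The note speaks of subjects, analysis is at subject level (SAP 4.1), and the rule for combining eyes is not visible. No error is shown there.

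**Existing safeguards.** Exclusions and reasons will be tabulated (SAP 4.5), robustness to losses and the impact of exclusions will be assessed (SAP 4.1, 4.7.6), and excluded and included subjects will be compared (SAP 4.7.7.4). These help, but none names this group and none changes the primary result.

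**Conclusion.** The inconsistency holds on the printed text. The note excludes on severity alone, while the SAP's definition makes definite edema sufficient for mtmDR. Any such subject with a device result is a known positive left out of the sensitivity denominator.

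The size is unknown. Under the assumed 237 positives, restoring up to five subjects moves the lower bound by at most about 1.9 points (79.6% to 77.7%), and hardly at all if the device detects them about as often as other positives. The pass or fail result changes only if observed sensitivity is near the pass mark and several of these subjects are missed. The conclusion rests on no exception existing in the Charter, the redacted block or Section 4.7.7.2. It does not extend to a claim that reported sensitivity is inflated, nor to the fellow-eye case.

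**What to change.** Replace the note in SAP 3.1 with: *Grade 90 subjects are excluded only when mtmDR status cannot be determined; a subject with definite macular edema on the W-4 grading is classed as mtmDR whatever the DR severity grade.* If the Charter or Section 4.7.7.2 already says this, cross-reference it in the note.

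Then make SAP 3.2, 4.1 and 4.4.1 consistent, so that evaluable according to the Reading Center means that mtmDR status could be determined. Report sensitivity with and without these subjects, and give their number. For a subject with one grade 90 eye, refer to the Charter's rule for combining eyes.

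The change uses grades that the Reading Center already produces and needs no new data. The cost is that reported sensitivity may be slightly less favourable.

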#### 3.2. Co-primary Effectiveness Endpoints

Sensitivity and specificity will be the co-primary effectiveness endpoints to be evaluated against FPRC determination (truth) in the ITS (Intent to Screen) population for whom IDx-DR provides a diagnostic result (primary) against pre-established standards (null hypotheses) to be rejected if too low relative to these pre-defined thresholds.

The computations for the sensitivity and specificity measures are displayed in Table 4.7.1. An mtmDR subject with a positive algorithm counts towards the sensitivity numerator while a Mild + No DR subject with a negative algorithm will count towards the specificity numerator. Every case will be accounted for in the sensitivity and specificity calculations.

### 3.3. Closed Testing Strategy

The closed testing strategy requires statistical significance to be separately met for both sensitivity and specificity

### 3.4. [REDACTED]

The IDx-DR Device and its algorithm will be locked prior to study launch. A version of the tested software will be placed in third-party escrow during the study, and will be available for comparison to the algorithm used in the study if questions of algorithm alterations arise. [REDACTED]  
[REDACTED]  
[REDACTED]  
[REDACTED]

### 3.5. Enrichment Strategy

Prospective enrichment will be used. [REDACTED]  
[REDACTED]  
[REDACTED]. Comparability will be assessed

using two-sided 95% confidence intervals for the respective cohorts.

### 3.6. Key Assumptions

The following assumptions govern sample size:

- [REDACTED]  
[REDACTED].
- The algorithms will be locked prior to subject enrollment.
- [REDACTED].
- The primary population for analysis will be patients from the Intention to Screen (ITS) population that have an IDx-DR result and a reference standard from the Reading Center.
- [REDACTED]  
[REDACTED]  
[REDACTED].
- To address incomplete data, prospective rules for case inclusion are summarized (see Section 4.7.7.2)

Both sensitivity and both specificity must achieve statistical significance to support study success. This strategy preserves the overall Type I error.

The statistical assumptions that were used to plan the study are as follows:

- Sample size calculations were performed at the subject-level.
- Use of conservative one-sided hypothesis testing with overall one-sided 2.5% Type I error [REDACTED]  
[REDACTED].
- The null hypotheses will be tested separately for mtmDR sensitivity and mtmDR specificity.
- All combined mild DR + no DR subjects will be included in the mtmDR specificity calculation. All mtmDR [REDACTED] subjects will be included in the more than mild DR sensitivity calculation.
- Subjects that received a IDx-DR result of "Insufficient Exam quality" will be excluded from primary analysis. [REDACTED]  
[REDACTED]  
[REDACTED]

[REDACTED]  
 [REDACTED]  
 [REDACTED]. As with all subjects, these subjects will also have been imaged using a 4-W protocol, with the wide field photos used by the FPRC to determine the reference standard.

### 3.7. Hypothesis Tests

The null hypotheses to be tested against a higher alternative hypothesis for the ITS population follow:

- mtmDR sensitivity:  $\leq 75\%$  null hypothesis vs  $>75\%$  alternative hypothesis ([REDACTED])
- mtmDR specificity:  $\leq 77.5\%$  null hypothesis vs  $>77.5\%$  alternative hypothesis ([REDACTED])

[REDACTED]  
 [REDACTED]  
 [REDACTED]  
 [REDACTED]  
 [REDACTED]  
 [REDACTED]  
 [REDACTED]  
 [REDACTED]  
 [REDACTED]  
 [REDACTED]  
 [REDACTED]  
 [REDACTED]  
 [REDACTED]  
 [REDACTED]  
 [REDACTED]

	[REDACTED]	[REDACTED]
[REDACTED]	[REDACTED]	[REDACTED]
[REDACTED]	[REDACTED]	[REDACTED]
[REDACTED]	[REDACTED]	[REDACTED]
[REDACTED]	[REDACTED]	[REDACTED]

[REDACTED]

[REDACTED]

	[REDACTED]	[REDACTED]
[REDACTED]	[REDACTED]	[REDACTED]
[REDACTED]	[REDACTED]	[REDACTED]

### 4. STATISTICAL METHODS

This analysis plan describes the planned data analyses.

#### 4.1. General Considerations

- This Statistical Analysis Plan (SAP) is based on the Clinical Trial Protocol for **A MULTICENTER STUDY TO EVALUATE PERFORMANCE OF AN AUTOMATED DEVICE FOR THE DETECTION OF DIABETIC RETINOPATHY AND DIABETIC MACULAR EDEMA** dated May 2017.
- All calculations will be performed using SAS statistical software, version 9.1 or later, and StatXact, version 10 or later.
- Final analysis will be conducted after the last subject completes evaluation by the RC.
- Analyses will be conducted at the subject-level (since both eyes are required to run the IDx algorithm).
- Study data will be used to simultaneously evaluate the mtmDR algorithm with study success defined to be rejecting both study hypothesis (see Section 4.7).
- All hypothesis tests will account for all subjects as previously stated (see Section 3.6).
- Testing will be performed for the ITS population for whom IDx-DR delivers a screening result and full ITS (secondary) to support labeling.
- To be included in ITS effectiveness analyses, subjects must be declared evaluable according to the FPRC and have a valid IDx-DR test.
- To be included in the primary effectiveness analyses, subjects must be declared evaluable according to the FPRC and have an IDx-DR screening test result.
- One-sided 2.5% Type 1 error was used to plan sample size.
- One-sided  $p=0.025$  will be required to achieve statistical significance for effectiveness; no p-value adjustment will be made for testing effectiveness endpoints since both specificity and sensitivity criteria must be met for study success.
- There are 18 effectiveness endpoints of interest (see Section 4.7.4) with two primary and six secondary endpoints.
- The literature suggests that there will be five times as many no DR cases as mild DR cases.
- The effect of subject losses will be assessed using robustness analyses for the two primary effectiveness endpoints (specificity and sensitivity).
- Verification bias will be investigated in excluded subjects.
- All effectiveness analyses will be performed using the ITS population for who IDx-DR delivers a screening result. Additional analyses will support labeling claims in the absence of a diagnostic result due to low quality imaging in a PCP setting by previously untrained ophthalmic photographers.
- Enriched subjects will be analyzed in combination with other subjects as well as separately to assess their impact.

#### 4.2. Study Objectives

The study objectives are to establish mtmDR specificity and the corresponding sensitivity.

#### 4.3. Photo Acquisition

The study population is described at the subject level. All subjects will be evaluated by photography and these photos will be subsequently evaluated via IDx-DR so no formal safety events are expected. Subjects may be reimaged per the IDx-DR imaging procedure if the initial image quality is not sufficient and the subject is willing to be retested.

#### 4.4. Analysis Populations

The following database components will be used to determine effectiveness analysis population inclusion:

- Subject eligibility
- IDx-DR results

- FPRC evaluation.

Each data source will be reviewed by the Contract Research Organization (CRO) for the algorithm processing and results reflecting input from appropriate medical, clinical, data management, and statistical personnel. Subject inclusion / exclusion status with respect to the study populations will be made without knowledge of IDx-DR outcome.

#### 4.4.1. Intent-to-screen (ITS) Population

The ITS population is described at the subject level and represents all eligible subjects with a Reading Center reference standard result. Study eligibility will be ascertained to exclude ineligible subjects from the ITS population. The primary study analyses will include the ITS population for whom IDx-DR delivers a screening output (i.e., a result of mtmDR or no/mild DR). Additional ITS population analyses will be confirmatory relative to these primary analyses for assessment of effectiveness, with reference standard established by the FPRC, which will determine the DR category each subject belongs to:

[REDACTED]

Rules regarding ITS exclusion decisions will be prospectively established prior to database lock and reviewed by individuals without knowledge of the IDx-DR outcome by subject.

